16.0 Potential Benefits to Subjects or Others

The experimental groups may benefit from receiving a respiratory training intervention. Respiratory training directly targets the respiratory system and *could* lead to greater improvements in both respiratory and voice outcomes than those observed with voice therapy alone.

There is a possibility that the participant will not directly benefit from being part of this research project.

For the subjects of the study, as well as for future voice patients who could benefit from this intervention if it were to be proven effective and to be implemented in common usual care, it could lead to important benefits:

- Improved respiratory and voice outcomes;
- Greater improvements in a person's daily activities involving communication;
- Reduced number of voice therapy sessions needed
- Improved voice-related quality of life

Because communication is a social activity, these benefits are also susceptible to impact the quality of life of the participants' significant other, family and caregiver.

The minimal risks associated with this research project are reasonable in relation to the potential benefits to the study participants and others. In the case where the intervention is not shown to be more efficacious than voice therapy only, the subjects would still receive the benefits from standard of care voice therapy.

Participant-raters will be compensated at a rate of \$40 for every 10-rating package (one package includes an endoscopy recording and an audio file). It is estimated that each rater will rate a total of 39 packages, for a total of \$160 for their participation in the study.

Both patient participants and participant raters may indirectly benefit, along with other patients, clinicians and society from the dissemination and implementation of the results of this research. The results of this research if in-line with our pilot data, will provide evidence that will serve as a guide for speech-language pathologists to inform patient management decisions. In general, any study that improves the effectiveness of voice intervention and the evidence upon which treatment recommendations are based may improve the health status and quality of life of patients and decrease the economic burden of voice disorders. These benefits outweigh the minimal risks that may result from loss of confidentiality and discomforts associated with the respiratory training interventions.

Importance of the Knowledge to be Gained

The paucity of evidence supporting the therapeutic benefit of respiratory training for patients with voice disorders is concerning considering their widespread use by speech language pathologists (SLPs) (58, 59). Despite the well documented relationship between the respiratory and laryngeal systems, evidence-based guidelines for respiratory training are non-existent in the field of voice therapy. This void represents a critical barrier to optimal care for patients with voice disorders, especially for patients with presbyphonia who have known respiratory declines due to aging.

Current breathing exercises used by SLPs, such as diaphragmatic breathing, increasing extent of thoracic expansion, and increasing period of expiratory airflow on phonemes /s, z, a, æ, i/(29, 60) have not been tested in clinical trials with voice patients. It is likely that most of these exercises are not adequately intensive, in terms of loading, to induce neuromuscular and hypertrophic changes necessary for improving

respiratory muscle strength. Despite this lack of evidence, many clinicians devote substantial time in their therapy sessions to these 'breathing exercises'. In-person therapy time with a SLP is already limited and therefore should not be spent on subthreshold 'breathing exercises', such as diaphragmatic breathing, that lack evidence. If respiratory training does improve function, it would give clinicians an alternative modality to substitute for less evidenced 'exercises' and change current practice by encouraging SLPs to administer an evidence-based respiratory training. In addition, results from this study would allow to identify profiles of patients likely to benefit from respiratory and more precisely from inspiratory or expiratory training, further promoting efficient and impairment-specific allocation of therapy time.

Conversely, negative findings from this study would raise questions about the relevance of respiratory training in patients with presbyphonia and help focus research as well as clinical practice on more effective treatment approaches. If adequately rigorous respiratory training does not produce sufficient improvement in vocal function, it would be a mandate to stop wasting treatment time on subthreshold 'breathing exercises'.

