Specific Aim 1: To measure the effects of respiratory training on respiratory and voice outcomes in patients with presbyphonia. Hypothesis 1: The respiratory training groups (inspiratory and/or expiratory) will demonstrate greater improvement in respiratory outcomes, measured through pulmonary function tests and respiratory pressure measures, compared with the voice exercises-only group. Hypothesis 2: The respiratory training groups (inspiratory and/or expiratory) will demonstrate greater improvement in voice-related outcomes than the voice exercises-only group.

Secondary Aim 1: To assess the reliability of the ratings for subjective outcomes (videostroboscopy ratings and perceptual judgements of voice quality). Hypothesis 1: Intra-judge reliability will be of at least 80%. Hypothesis 2: Inter-judge reliability will be of at least 70%.

Specific Aim 2: To determine how baseline measures of respiratory function influence the effects of respiratory training (respiratory and voice outcomes). Hypothesis 1: inspiratory training will have maximal effect on patients with decreased maximum inspiratory pressure (MIP). Hypothesis 2: Expiratory will have maximal effect on patients with decreased maximum expiratory pressure (MEP).

This is an initial feasibility and mechanistic study that has the potential to reveal that respiratory training can significantly improve outcomes from voice therapy by acting in synergy with voice exercises. Currently,

much time is spent in voice therapy on subthreshold 'breathing exercises' that lack evidence. This project will provide guidance for evidence-based and theory driven approaches to leverage respiratory function to improve voice therapy. Conversely, negative findings from this study would indicate that respiratory function is ineffective and not a viable target for therapy in this patient population.

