6.0 Number of Subjects

Forty-eight patients-participants and up to six raters-participants will be recruited for the study.

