Raters will rate the audio recordings with the CAPE-V form and the videostroboscopy images with the VALI form. They will rate pre- and post-intervention de-identified recordings for each participant, and an additional sampling of 20% of the recordings (for intrarater reliability testing).

Data Collection

Data collected will be the same for Aim 1 and Aim 2. It will include information in the patient's medical record (obtained from standard of care assessment) and obtained through a demographic questionnaire as well as clinical data using standardized collection instruments: spirometry measures, muscle pressure measures and acoustic assessment.

Each video and audio recording will be de-identified when videos are converted into .mpg, .nsp or .mp3 files before distributing the recordings via Box for analysis. Participant raters will review the de-identified digitized recordings for the purposes of data collection and score each video and audio recording using the VALI and CAPE-V rating forms, respectively.

Spirometry, muscle pressure data, and voice data will be recorded in a data collection sheet by the study team member. Data collection sheets will be labeled with the alphanumeric identifier of the patient-participant. Completed data collection sheets, with ratings from the CAPE-V and VALI, will be entered in the database by a study team member. Research records will be retained for a period of six years to allow evaluation and repetition of the results by others.

Study personnel will enter mandatory data fields for demographics according to the NIH minimum standards for maintaining, collecting and presenting data on gender, race and ethnicity. The demographic and clinical data will be exported for analysis.

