12.0 Data Management

Data Analysis Plan

Demographic characteristics will be compared across the 3 intervention groups, using a RxC contingency table method for categorical variables (gender, smoking history, voice use, racial and ethnic category) and a one-way ANOVA for continuous variables (age, weight, height). Baseline characteristics will be compared across the 3 intervention groups using a Kruskal-Wallis one-way analysis of variance by ranks for ordinal data (GFI, RSI, and VHI scores), a RxC contingency table for categorical variables (glottal gap shape, free edge contour, vertical level, phase closure) and a one-way ANOVA for continuous variables. Aim 1: To assess the effects of respiratory training on voice and respiratory outcomes in patients with presbyphonia. Data will be analyzed on an intention-to-treat basis using multifactor repeated measures generalized linear regression. Distributional assessment will be made for each outcome to confirm optimal distributional assignment and potential need for outcome transformation (i.e. log link). In the model, the repeated factor is time, which has two levels (pre- or post-intervention) and the independent factor is the intervention, which has three levels (IMST, EMST, VFE). In the case of a significant between-subjects effect, multiple comparison tests will be conducted to determine which groups differ. The post-hoc analysis will be done using Tukey's honestly significant difference (offering protection against type I error without being too conservative). Spearman and Person correlations will be calculated to establish inter and intrarater reliability. Aim 2: To identify profiles of presbyphonic patients that would benefit the most from respiratory training. Logistic regression will be conducted to predict which patients improved following inspiratory training and which patients improved following expiratory training, based on their baseline clinical characteristics. Two outcome variables will be indicative of meaningful clinical improvement: 1) MPT (to measure function), and 2) GFI (to measure patient perception of function). Meaningful clinical improvement will be defined by an increase of at least 4 seconds in MPT or a decrease of at least 4 points in GFI score. Participants will be dichotomized as having meaningful clinical improvement, or not, based on these outcomes. Predictors will include MIP, MEP, maximum SPL, breaths per minute, FVC, FEV1, and P_s. These measures were chosen because they are directly influenced by the integrity of the respiratory system.

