Unknown risks: Respiratory training has never been tested on patients with presbyphonia. The results of this combination are unknown. Although unlikely, there is a slight risk that unforeseen adverse events could result from this combination.

Protections Against Risk

Loss of confidentiality: Protection against the loss of confidentiality will be diminished by 1) completing study aims at one data collection site, 2) minimizing the participants involved to only those needed to accomplish the study aims (see sample size justification above), 3) de-identifying data at the earliest opportunity, and 4) maintaining stored data in locked/password protected locations whose access is restricted to members of the study team. All data collection and study activities will be conducted at MUSC. The patient subject sample will include up to 48 patients referred for a videostroboscopy within the scope of their usual care at MUSC and who meet the inclusion criteria. The sample will be limited to the MUSC site because historical accruals have been shown sufficient to meet power (see participant section above). Six participant raters will be recruited from SLPs who have experience with voice disorders. An alphanumeric identifier will be used instead of patient participant name and rater participant name at the earliest possibility. In order to ensure participant's confidentiality, database entry will be password protected and study documents will be maintained in a locked cabinet in the PIs locked office. Patient identity will also be protected by confidentiality policies and procedures already in place at the MUSC site. A participant may withdraw from the study at any time without penalty or prejudice.

Spirometry and muscle pressure testing: If the patient-participant manifests signs of discomfort or dizziness, the spirometry or muscle pressure testing maneuver will be interrupted following the American Thoracic Society's (ATS) recommendations(47). Stopping the maneuver will avoid a syncope, which could follow due to the interruption of venous return to the thorax during prolonged exhalation. As a precaution, all assessments will be done in a sitting position, in a chair with arms and without wheels to prevent falls.

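### About two of six raters score each recording, and nothing keeps a participant's pre and post recordings with the same raters, so rater severity can enter the CAPE-V and VALI change scores

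*Combined protocol and SAP*

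**What the plan says.** Section 10.0 (Rater Participants) describes the rating task: "They will rate pre- and post-intervention de-identified recordings for each participant, and an additional sampling of 20% of the recordings". Section 16.0 gives the load per rater, "It is estimated that each rater will rate a total of 39 packages", and explains that "one package includes an endoscopy recording and an audio file". Section 6.0 allows for "up to six raters-participants will be recruited for the study", while Section 15.0 is definite: "Six participant raters will be recruited from SLPs who have experience with voice disorders".

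The Section 10.0 overview blinds the judges to group assignment and says nothing about time point. Secondary Aim 1 in Section 1.0 sets the targets: "Intra-judge reliability will be of at least 80" per cent, and 70% between judges. Section 12.0 gives the method: "Spearman and Person correlations will be calculated to establish inter and intrarater reliability". The Aim 1 model in the same section contains time (two levels) and intervention (three levels) and nothing for rater.

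No section states how many raters score a recording, how recordings are allotted to raters, whether the same raters score both of a participant's recordings, or how several ratings become one score.

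**The concern.** Read literally, Section 10.0 has every rater score every recording. In that complete design each rater's severity applies equally before and after treatment and cancels from the change. The workload in Section 16.0 rules that design out. With only some of the raters scoring each recording, severity cancels only when the same raters score both visits, and the plan does not require this.

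CAPE-V and VALI are the only outcomes for which the plan describes blinded assessment. They contribute to Aim 1, Hypothesis 2 and are the whole of Secondary Aim 1. In a study of 48 people in three arms, avoidable noise in these scores matters. The reliability check is the natural place to discover a severity problem, but it uses a statistic that does not respond to one.

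**Working it through.** **Inputs.** 48 participants (Section 6.0); two recordings each plus a 20% repeat sample (Section 10.0); six raters (Section 15.0); 39 packages per rater (Section 16.0).

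**Step 1: reproduce the plan's figure.** Packages per rater = 48 × 2 × 1.2 × k / R, with k raters per recording and R raters in all.
- Total packages: 48 × 2 × 1.2 = 115.2.
- R = 6: k = 1 gives 19.2; k = 2 gives 38.4, which rounds up to 39; k = 3 gives 57.6; k = 6 gives 115.2.
- In reverse: 6 × 39 = 234 ratings, and 234 / 115.2 = 2.03 per recording.
- Payment agrees: 39 packages fill four lots of ten, and 4 × $40 = $160, the stated total.
- With 45 completers: 234 / (45 × 2 × 1.2) = 2.17, still about two.
- If only three raters were recruited, which Section 6.0 permits, 3 × 39 / 115.2 = 1.02. That leaves almost no overlap for inter-judge reliability.

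**Step 2: does 39 exclude pairing?** No. If each rater takes 16 participants at both visits, the load is 16 × 2 × 1.2 = 38.4, the same figure.

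**Step 3: cost of not pairing.** The documents give no variance components, so these are assumptions: single-rating variance 1; participant share 0.70; rater severity share r from 0.05 to 0.25; residual share 0.30 − r; true pre/post correlation ρ from 0.5 to 0.7; the outcome is the mean of two ratings.
- Same raters at both visits: V = 2 × 0.70 × (1 − ρ) + (0.30 − r).
- Wholly different raters: V + r.
- Two of six drawn afresh at each visit: V + r × (1 − 2/6).

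| r | ρ | V | Random draw, ratio | Wholly different, ratio |
|---|---|---|---|---|
| 0.05 | 0.5 | 0.95 | 0.983 / 0.95 = 1.04 | 1.00 / 0.95 = 1.05 |
| 0.25 | 0.7 | 0.47 | 0.637 / 0.47 = 1.35 | 0.72 / 0.47 = 1.53 |

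These rows are the ends of the range. A standardised effect shrinks by one over the square root of the ratio: to 0.98–0.86 of its value with a random draw, and to 0.98–0.81 with wholly different raters.

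**Step 4: would the planned check reveal it?** If one rater scores a constant c above another, their Pearson and Spearman correlations are the same whatever c is. Repeats by one rater carry no information on differences between raters.

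**Step 5: precision of reliability (95% Fisher-z intervals).** Two raters per recording gives 96 × 2 / 6 = 32 first ratings per rater, leaving 39 − 32 = 7 repeats.
- Intra-rater r = 0.80, one rater, 7 repeats: 0.12 to 0.97.
- Intra-rater r = 0.80, pooled over 6 × 7 = 42 repeats: 0.66 to 0.89.
- Inter-rater r = 0.70, pooled over 96 recordings: about 0.58 to 0.79.

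The pooled intervals treat the pairs of ratings as independent, so they are approximate.

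**The case against.** The strongest reply is that the 39 packages fit a paired design exactly, and that Section 10.0 can be read as the raters, as a group, covering both recordings of each participant. On that reading the two sections do not conflict and severity may cancel in practice. This stands as far as it goes: contamination is possible, not established. It does not remove the gap, because no sentence requires pairing.

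The documents do not support several stronger conclusions that a reader might draw.
- **A two- or sixfold rise in error.** The ratio 0.30 / (0.30 − r) gives 1.2, 2 or 6 for r of 0.05, 0.15 or 0.25. It covers only the rating-error part of the change and leaves out variation in true change. It also assumes wholly different raters at the two visits, which a random draw of two from six produces in only 6/15 = 40% of cases.
- **Bias between arms.** Raters are blinded to group. Nothing in the plan links rater to arm, so random assignment costs precision and creates no expected bias.
- **Reliability targets that cannot be judged at all.** With all 15 rater pairs analysed separately, each shares 96 / 15 = 6.4 recordings, and r = 0.70 on 6 has an interval of −0.26 to 0.96. The plan does not say that pairs will be analysed separately, and the pooled interval is usable.
- **The video colouring the voice score.** Section 16.0 defines a package as a payment unit. It does not say that its two files come from the same participant and visit.

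It is also fair that the reach is limited. Sample size rests on MPT, Aim 2 on MPT and GFI, and the study describes itself as an early feasibility and mechanistic one.

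**Conclusion.** The point holds as a gap in design and analysis affecting CAPE-V and VALI. With six raters the plan's own workload means about two ratings per recording. Pairing of visits, blinding to time point and a rater term are all absent, so rater severity can enter the change scores.

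With random assignment the consequence is lost precision, within the ranges in the table. Those ranges rest wholly on the assumed variance shares and pre/post correlation. It becomes bias in the time effect only if ratings are batched by visit, and bias in the arm contrast only if rater assignment differs by arm.

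The planned correlations would not show a severity shift, and about 7 repeats per rater are too few to judge the 80% target rater by rater. The arithmetic on workload is secure; the size of the loss is illustrative.

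**What to change.** - Reconcile Sections 10.0 and 16.0 by stating two raters per recording, and Sections 6.0 and 15.0 by fixing the number of raters at six.
- Assign both recordings of a participant, and any repeat, to the same two raters. Balance raters across arms from a list prepared by someone who does not rate: 16 participants × 2 raters / 6 gives 5 or 6 participants per arm for each rater.
- Present clips in random order with the time point hidden.
- Analyse the mean of the two raters' scores, or add a rater random effect to the Aim 1 model. State which rating of a repeated recording enters the outcome.
- Replace the correlations with an absolute-agreement ICC, with its confidence interval, from one variance-components model pooled over all raters.

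The cost is a rating schedule, a few sentences of analysis text and slightly more work preparing packages. Mixing the visits at random also means that a participant's pre recording waits until the post recording exists. No extra raters or ratings are needed, since the paired load is 38.4 packages per rater against the 39 already budgeted. This should be settled before rating starts: once ratings have been collected unpaired, a rater term recovers only part of the loss.

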17.0 Sharing of Results with Subjects

During the course of the experimental sessions, the study team member will discuss the evolution of the respiratory outcomes with the participant. At the conclusion of the study, a study team member will offer to send an email to interested participants, with the findings from the study.

